## 8 Trial Schedule and Assessments

### 8.1 Schedule of Trial Procedures

**Table 1: Schedule of Trial Procedures – Non-HPA Axis Cohort**

**Note:** Separate schedule of trial procedures for subjects in the HPA axis cohort below.

Visit	SV1 	SV2 	1	2	3	EW	FU 
Day	-28 to -7	-7 to -3	0	14 ± 2	28 ± 2	--	+ 14 ± 2
Informed consent	X						
Demographics	X						
Medical history and concurrent diagnoses	X						
Physical examination	X				X	X	
Height, weight and BSA 	X		X				
Inclusion/exclusion criteria	X	X	X				
Vital signs (blood pressure, heart rate, oral or ear temperature)		X	X	X	X	X	
25-hydroxy Vitamin D		X					
Haematology/biochemistry/urinalysis 		X			X	X	X 
Instructions for dietary calcium intake diary	X			X			
Review of dietary calcium		X			X	X	
Urine pregnancy test 		X			X	X	
Adverse events		X	X	X	X	X	X
Local safety and tolerability			X	X	X	X	
Concomitant medication	X	X	X	X	X	X	X
Physician's assessment of extent of psoriasis vulgaris		X	X		X	X	
Physician's assessment of extent of body psoriasis		X	X		X	X	
Physician's assessment of extent of scalp psoriasis		X	X		X	X	
Physician's global assessment of disease severity on the body		X	X	X	X	X	
Physician's global assessment of disease severity on the scalp		X	X	X	X	X	
Physician's assessment of the extent and severity of clinical signs of psoriasis vulgaris (for PASI)		X	X	X	X	X	
Subject's global assessment of disease severity on the body		X	X	X	X	X	
Subject's global assessment of disease severity on the scalp		X	X	X	X	X	
Subject's assessment of itch and itch-related sleep loss			X	X	X	X	
CDLQI 			X	X	X	X	
FDLQI 			X		X	X	
Dispensing of IP			X	X			
Return of IP				X	X	X	
IP Compliance				X	X	X	

- 1) There should be at least 4 days between SV1 and SV2 so dietary information (diary) can be collected.
- 2) Follow-up Visit 1 is only applicable for subjects who at the last on-treatment visit have an ongoing Serious Adverse Event of any causality or ongoing non-serious adverse event(s) classified as possibly/probably related to the investigational product and for subjects with albumin corrected serum calcium above reference range at the last on-treatment visit.
- 3) Body surface area (BSA) to be calculated using the Mosteller formula ([Appendix 9](#)).
- 4) Blood and spot urine samples should be collected at the end of treatment for subjects who are withdrawn from trial prior to Visit 3.

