**Table 2: Schedule of Trial Procedures – HPA Axis Cohort**

Visit	SV1 	SV2 	1	2	3	EW	FU1 	FU2 
Day	-28 to -7	-7 to -3	0	14 ± 2	28 ± 2	--	+ 14 ± 2	+ 28 ± 2
Informed consent	X							
Demographics	X							
Medical history and concurrent diagnoses	X							
Physical examination	X				X	X		
Height, weight and BSA 	X		X					
Inclusion/exclusion criteria	X	X	X					
Vital signs (blood pressure, heart rate, oral or ear temperature)		X	X	X	X	X		
25-hydroxy Vitamin D		X						
Cortisol (serum)		X			X			
Haematology/biochemistry/urinalysis 		X			X	X	X 	
Pharmacokinetic sampling 				X	X			
ACTH challenge test 		X			X			X
Instruction for 24-hour urine collection 	X			X				
Instructions for dietary calcium intake diary	X			X				
Review of dietary calcium		X			X	X		
Collection of 24-hour urine 		X			X			
Urine pregnancy test 		X			X	X		X
Adverse events		X	X	X	X	X	X	X
Local safety and tolerability			X	X	X	X		
Concomitant medication	X	X	X	X	X	X	X	
Physician's assessment of extent of psoriasis vulgaris		X	X		X	X		
Physician's assessment of extent of body psoriasis		X	X		X	X		
Physician's assessment of extent of scalp psoriasis		X	X		X	X		
Physician's global assessment of disease severity on the body		X	X	X	X	X		
Physician's global assessment of disease severity on the scalp		X	X	X	X	X		
Physician's assessment of the extent and severity of clinical signs of psoriasis vulgaris (for PASI)		X	X	X	X	X		
Subject's global assessment of disease severity on the body		X	X	X	X	X		
Subject's global assessment of disease severity on the scalp		X	X	X	X	X		
Subject's assessment of itch and itch-related sleep loss			X	X	X	X		
CDLQI 			X	X	X	X		
FDLQI 			X		X	X		
Dispensing of IP			X	X				
Return of IP				X	X	X		
IP Compliance				X	X	X		

- 1) There should be at least 4 days between SV1 and SV2 so dietary information (diary) can be collected.
- 2) It will be acceptable that the following assessments are done on the day prior to the ACTH challenge: vital signs, spot urine collection, pregnancy test, AEs, concomitant medication and assessments of psoriasis.

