## 9.1 Collection of Adverse Events

Adverse events must be collected from the signing of the informed consent form until the End of the trial (Visit 3, Day 28).

AEs must be assessed by medically qualified personnel.

At all visits, the subject will be asked a non-leading question by the (sub)investigator: “How have you felt since I saw you last?” No specific symptoms should be asked for. It is important that the (sub)investigator also observes the subject for any changes not reported by the subject and records these changes.

If there are no AEs to record, no further questions should be asked and “NO” should be stated in the CRF. In case there are one or more AEs to record, “YES” should be stated.

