## 9.2 Reporting of Adverse Events in the CRF

Adverse events reported by the subject or observed by the (sub)investigator must be recorded on the adverse event form of the CRF and should be described in the following manner:

The *AE term* will be in precise English medical terminology (i.e. not necessarily the exact words used by the subject). Whenever possible, a specific diagnosis should be stated (e.g. allergic contact dermatitis).

For cutaneous AEs the *location* must be part of the AE description and may be described as either the face, scalp or trunk/limbs. Additionally, the location should be described using the following terminology:

- Lesional/perilesional ( $\leq 2$  cm from the border of lesion(s) treated with investigational product) or
- distant ( $>2$  cm from the lesion border)

The *duration* of the AE must be reported as the start date and stop date of the event. In addition, it must be recorded whether the AE started prior to start of trial medication.

AEs must be classified in terms of severity, causality and outcome according to the definitions in [Appendix 3 Classification of Adverse Events](#)

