### **9.5 Additional Reporting Requirements for Serious Adverse Events**

#### **9.5.1 Investigator Reporting Responsibilities**

Any Serious Adverse Event (SAE) must be reported to LEO on the (paper) Serious Adverse Event Form – Clinical Trials within 24 hours of first knowledge. This report should contain an assessment of available information on seriousness, severity, causal relationship to the investigational product, comparator or trial procedure, the action taken, the outcome to date, and a narrative description of the course of the event.

The completed SAE form must be faxed or scanned and e-mailed to Global Pharmacovigilance, LEO using the following fax number or e-mail address:

[contact] (for Global Pharmacovigilance)

E-mail address: [[contact]](mailto:[contact]) (for Global Pharmacovigilance).

It may be relevant for the (sub)investigator to enclose other information with the SAE form, such as reports of diagnostic procedures, hospital records, autopsy reports, etc.

Additionally, Global Pharmacovigilance, LEO may request further information in order to fully assess the SAE. The (sub)investigator must forward such information to Global Pharmacovigilance, LEO upon request by fax or e-mail (see contact details above).

The investigator must notify the local IRB(s)/IEC(s) of SAEs as required by current applicable legislation for the concerned country.

SAEs occurring after the completion of the clinical trial including any protocol required post-treatment follow-up period should not be routinely sought or collected. However, such events should be reported to Global Pharmacovigilance, LEO ([contact]) if the (sub)investigator becomes aware of them.

The criteria qualifying the AE to be an SAE should be recorded in the CRF (see section [26.2, Appendix 2](#)).

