## 9.6 Follow-up for Final Outcome of Adverse Events

During the trial, the investigator should follow up for final outcome on all AEs (including SAEs). Once a subject leaves the clinical trial, the investigator should follow up on the outcome of all non-serious AEs classified as of possible/probable relationship to the investigational product for  $14 \pm 2$  days or until the final outcome is determined, whichever comes first. SAEs must be followed up until a final outcome has been established, i.e. the follow-up may continue beyond the end of the clinical trial.

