Main assessments	
Safety Assessment
 
Laboratory analysis:
 
the following laboratory tests will be taken at SV2 and Visit 3 (Day 28).
 

• haematology: hemoglobin, haematocrit, red blood cells (RBC), mean corpuscular volume (MCV), white blood cells (WBC) including differential count and platelets.

• biochemistry (serum/plasma): cortisol (only for subjects in HPA Axis Cohort), urea, creatinine, albumin, sodium, potassium, chloride, calcium, phosphate, ALP and PTH.

• urinalysis on 24-hour urine: calcium, phosphate, creatinine, volume.

• urinalysis on spot urine: glucose, ketones, calcium, phosphate and creatinine

 
At SV2 only, the vitamin D status will be assessed by the following laboratory analysis:
 

• 25-hydroxy vitamin D

 
Calcium metabolism evaluation will include serum albumin-corrected calcium, phosphate, alkaline phosphatase (ALP) and plasma parathyroid hormone (PTH) on a blood sample taken at SV2 and after 4 weeks of treatment.
 
24-hour urine (only for subjects undergoing HPA axis testing) and spot urine will be collected at SV2 and after 4 weeks of treatment and urinary volume, calcium-, phosphate-, and creatinine excretion will be measured and calcium:creatinine and phosphate:creatinine ratios will be calculated.
 
Dietary calcium intake will be monitored 3 days prior to and during collection of 24-hour urine/spot urine collection. Subjects will be instructed to keep a diary of daily intake of calcium-rich nutrients in these periods.
 
ACTH challenge test:
 
For subjects performing HPA axis assessments: the ACTH challenge test will be performed on 2 occasions: At SV2 and Visit 3 (Day 28). In addition, an ACTH challenge test will be performed at Visit FU2 for subjects with possible HPA axis suppression at Visit 3.
 
Vital signs:
 
Blood pressure and temperature will be measured at SV2 and Visit 3 (Day 28).
 
Adverse events:
 
Adverse events will be recorded at all visits after SV1 (if applicable).
 
Assessment of Local Safety and Tolerability
 
At all treatment phase visits, the Assessment of Local Safety and Tolerability will comprise of perilesional signs of erythema, oedema, dryness and erosion assessed by the (sub)investigator.
 
For each sign the highest (worst) skin reaction score across all treatment areas will be recorded by use of a 4-point scale:
 
Pregnancy test:
 
Urinary pregnancy test will be performed at SV2, Visit 3 (Day 28) and at FU2 (if applicable) in

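### Protocol 9.1 ends AE collection at Visit 3 although the schedule carries it to FU1 and FU2, and 7.8 omits the ACTH test from its early-withdrawal exceptions

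*Protocol*

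**What the plan says.** **AE collection.** Protocol 9.1 sets the period: "Adverse events must be collected from the signing of the informed consent form until the End of the trial (Visit 3, Day 28". The same section continues: "At all visits, the subject will be asked a non-leading question by the (sub)investigator". Table 1 marks AEs in its FU column, and "Table 2: Schedule of Trial Procedures – HPA Axis Cohort" marks them at both FU1 and FU2. Appendix 1 states: "Adverse events will be recorded at all visits after SV1 (if applicable". Section 9.2 adds a general duty with no end date: "Adverse events reported by the subject or observed by the (sub)investigator must be recorded on the adverse event form of the CRF". Section 16.1 defines end of trial as the date of the last subject's last visit, which is not Visit 3.

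**Who is followed up.** A footnote to Table 1 begins: "Follow-up Visit 1 is only applicable for subjects who at the last on-treatment visit have an ongoing Serious Adverse Event of any causality". It goes on to add ongoing non-serious AEs judged related and albumin-corrected calcium above range. Under 6.1, FU2 is only for subjects whose 30-minute cortisol at Visit 3 was 18 mcg/dl or lower.

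**Early withdrawal.** Section 7.8 requires the additional Visit 3 tests at the end of treatment for subjects who withdraw early, with the 24-hour urine as the only exception. Section 8.12.4 says the ACTH-challenge test is not to be done in that case. Table 2 has no mark under EW for the ACTH test, serum cortisol or PK sampling.

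**The concern.** Adverse events are a primary endpoint, and follow-up attendees return because of a safety signal: an ongoing event, raised calcium or low cortisol. Under the current text, whether a new non-serious event in one of them reaches the CRF depends on which instruction the site follows. Three kinds of event are exposed:

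- A delayed reaction to the last dose. Table 16 has product applied at Visit 3 after the assessments are finished.
- Mild symptoms after the steroid is stopped.
- A non-allergic reaction to the ACTH injection at FU2.

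The slip in 7.8 concerns subject protection more than estimation. A site that followed 7.8 alone would give an intravenous injection to a withdrawn adolescent that 8.12.4 rules out. Section 10.7.1.4 warns that repeat administration may raise the risk of hypersensitivity. The test would also not serve the cortisol endpoint, because the per protocol set in 11.2 requires a Week 4 result.

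**Working it through.** **1. The plan's own figure.** Section 11.1 gives 86.7% as the probability of at least one case among 100 subjects when the true frequency is 2%. Check: 1 − 0.98^100 = 0.8674. It reproduces. It depends on the frequency and the number of subjects, so neither correction below changes it.

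**2. How far follow-up lies beyond the 9.1 date.** Inputs are Visit 3 at Day 28 ± 2, FU1 14 ± 2 days later and FU2 28 ± 2 days later (6.1, Tables 1 and 2).

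- FU1: 28 + 14 = Day 42; earliest 26 + 12 = Day 38, latest 30 + 16 = Day 46.
- FU2: 28 + 28 = Day 56; earliest 26 + 26 = Day 52, latest 30 + 30 = Day 60.
- Nominal span outside 9.1: 42 − 28 = 14 days for FU1 and 56 − 28 = 28 days for FU2.

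Both visits always fall after the date in 9.1.

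**3. Do the follow-up marks only mean tracking of existing events?** Section 9.6 covers outcomes: "the investigator should follow up on the outcome of all non-serious AEs classified as of possible/probable relationship to the investigational product". That would account for an AE mark at an FU1 visit triggered by an ongoing event. It does not account for FU2, which is triggered by a cortisol value, or for an FU1 visit triggered by calcium alone. The schedule therefore expects AE assessment in subjects who may have no ongoing event.

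**4. What is left once other sections are counted.**

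- SAEs during required follow-up stay in scope, because 9.5.1 lifts the duty to seek them only afterwards: "SAEs occurring after the completion of the clinical trial including any protocol required post-treatment follow-up period should not be routinely sought or collected".
- Ongoing related non-serious AEs are followed for outcome under 9.6.
- An allergic reaction to the ACTH agent requires withdrawal (7.8, 10.7.1.4), and the reason goes into the CRF, so it is partly captured.
- New non-serious AEs with onset after Visit 3 in follow-up attendees have no protection other than the texts that contradict 9.1.
- Section 8.12.4 also provides for repeat ACTH tests after FU2 until suppression resolves. Table 2 stops at FU2 and so schedules no AE assessment at those tests.

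**5. Early withdrawal, Visit 3 tests side by side.**

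| Visit 3 test | 7.8 | 8.12.4 | Table 2, EW column |
|---|---|---|---|
| 24-hour urine | excepted | – | blank |
| ACTH challenge | not excepted | not to be done | blank |
| Serum cortisol | not excepted | – | blank |
| PK sampling | not excepted | – | blank |

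The Visit 3 volumes for the last three rows come from Table 10: 3 × 2.5 = 7.5 mL for ACTH, 2.5 mL for serum cortisol and 4 × 12 = 48 mL for PK. The sum is 7.5 + 2.5 + 48 = 58 mL. These samples would replace the Visit 3 samples, so the planned total of 98 mL would not be exceeded.

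**The case against.** The best reply is that one parenthesis in 9.1 stands against several texts that agree with each other. The schedule, the visit instruction in 9.1, the recording duty in 9.2, Appendix 1 and the definition in 16.1 all point to collection through follow-up. Appendix 2 counts events related to trial procedures as AEs, which includes a reaction at FU2. On early withdrawal, 8.12.4 is the section that governs the ACTH test, Table 2 agrees with it, and a footnote there limits sampling in withdrawn subjects to blood and spot urine. A careful site would probably act correctly in both cases. That stands, and it is why the effect is small. It does not remove the fault: 9.1 is the section that sets the collection period, and 7.8 is where a site looks when a subject withdraws.

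Three stronger readings are tempting, and the documents do not support them.

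- *The AE endpoint is biased.* Nothing shows that an event went unrecorded. SAP 6.3.3 reports no SAEs and no withdrawals due to AEs. SAP 6.3 drops the planned low-cortisol tabulations because too few subjects qualified.
- *The main AE tables need a cut-off at Visit 3.* The treatment-emergent definition in 11.3.8.1 has no end date, so a reader might want one. But a reaction starting the day after the Visit 3 dose would then leave the main tables. Start dates are recorded (9.2) and all AEs are listed, so late events can already be identified.
- *About one subject met the conflict in 7.8.* In SAP Table 2 the total for the 24-hour urine group goes from 34 to 33. The SAP gives no reason for the change and does not say that anyone withdrew early or was tested.

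**Conclusion.** Both contradictions are real and should be corrected. The first is confined to new non-serious AEs after Visit 3, in subjects who attend FU1, FU2 or a later repeat ACTH test, at a site that puts the parenthesis in 9.1 above the other texts. Subjects with no follow-up visit have no later scheduled contact, so neither the fault nor the correction concerns them. The documents give no count of follow-up attendees, so the number of exposed events cannot be stated. That it is small is inferred from the conditional triggers and the SAP remarks. The second is an incomplete list in 7.8. It does not touch the Week 4 cortisol endpoint, and it matters because it could prompt an injection that 8.12.4 rules out. Sample size and confidence intervals are unaffected.

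**What to change.** - **Protocol 9.1:** replace the parenthesis naming Visit 3 and Day 28 with each subject's last attended visit, including FU1, FU2 and any later repeat ACTH test.
- **Protocol 7.8:** add the ACTH-challenge test, serum cortisol and PK sampling to the early-withdrawal exceptions, to match 8.12.4 and Table 2.
- **Analysis:** leave the treatment-emergent tables in 11.3.8.1 and SAP 6.3.3 without a Visit 3 cut-off. At most, flag events with onset after Visit 3 in the AE listing (SAP Listing 7-5).

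The cost is two short wording changes and an optional flag in an existing listing. No visit is added, because AE assessment is already scheduled at FU1 and FU2. The only new recording is at ACTH tests after FU2, which the subject attends anyway.

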## 9.2 Reporting of Adverse Events in the CRF

Adverse events reported by the subject or observed by the (sub)investigator must be recorded on the adverse event form of the CRF and should be described in the following manner:

The *AE term* will be in precise English medical terminology (i.e. not necessarily the exact words used by the subject). Whenever possible, a specific diagnosis should be stated (e.g. allergic contact dermatitis).

For cutaneous AEs the *location* must be part of the AE description and may be described as either the face, scalp or trunk/limbs. Additionally, the location should be described using the following terminology:

- Lesional/perilesional ( $\leq 2$  cm from the border of lesion(s) treated with investigational product) or
- distant ( $>2$  cm from the lesion border)

The *duration* of the AE must be reported as the start date and stop date of the event. In addition, it must be recorded whether the AE started prior to start of trial medication.

AEs must be classified in terms of severity, causality and outcome according to the definitions in [Appendix 3 Classification of Adverse Events](#)

### 9.3 Actions Taken as a Consequence of an AE

*Action taken with trial treatment:* Any action taken with trial medication as a consequence of the AE must be recorded (dose not changed, dose reduced, dose increased, drug interrupted, drug withdrawn, not applicable, unknown).

*Other action taken:* Any other action taken as a result of the AE must be recorded (none, concomitant medication, concurrent procedure).

*Withdrawn due to AE:* It must be recorded whether the AE leads to withdrawal from the trial.

### 9.4 Other Events to be Reported

#### 9.4.1 Pregnancy

Any pregnancy occurring during the clinical trial must be reported to LEO within 24 hours of first knowledge using the (paper) Pregnancy Follow Up Form (Part I). All such pregnancies must be followed up until delivery or termination and final outcome must be reported on the (paper) Pregnancy Follow Up Form (Part II) within 24 hours of first knowledge.

The completed Pregnancy Follow Up Forms must be faxed or scanned and e-mailed to Global Pharmacovigilance, LEO (see section [9.5.1](#) for contact details).

Please also confer with section [7.8](#), Withdrawal Criteria.

#### 9.4.2 Overdose

Overdose refers to the administration of a quantity of a medicinal product given per administration or per day which is above the protocol defined dosage.

The term overdose must be documented on the adverse event form of the CRF book. In addition, AEs originating from overdose must be documented on a separate line.

#### 9.4.3 Medication Error

Medication error refers to any unintentional error in the dispensing or administration of a medicinal product while in the control of the (sub)investigator or subject. Broadly, medication errors fall into four categories: wrong medication, wrong dose (including strength, form, concentration, amount), wrong route of administration or wrong subject.

The medication error must be documented on the adverse event form of the CRF book. In addition, AEs originating from a medication error must be documented on a separate line specifying the category of error (see definitions above).

#### **9.4.4 Misuse**

Misuse refers to situations where the medicinal product is intentionally and inappropriately used not in accordance with the protocol.

The term misuse must be documented on the adverse event form of the CRF book. In addition AEs originating from misuse must be documented on a separate line.

#### **9.4.5 Abuse**

Abuse relates to the sporadic or persistent, intentional excessive use of an investigational product which is accompanied by harmful physical or psychological effects.

The term abuse must be documented on the adverse event form of the CRF book. In addition, AEs originating from abuse must be documented on a separate line.

#### **9.4.6 Aggravation of Condition**

Any clinically significant aggravation/exacerbation/worsening of any medical condition(s), compared to baseline, must be reported as an AE.

